## **11.7 Confidentiality of study documents and patient records**

The investigator must ensure anonymity of the patients; patients must not be identified by names in any documents submitted to Novartis. Signed informed consent forms and patient enrollment log must be kept strictly confidential to enable patient identification at the site.

## **11.8 Audits and inspections**

Source data/documents must be available to inspections by Novartis or designee or Health Authorities.

## **11.9 Financial disclosures**

Financial disclosures should be provided by study personnel who are directly involved in the treatment or evaluation of patients at the site - prior to study start.

## **12 Protocol adherence**

Investigators ascertain they will apply due diligence to avoid protocol deviations. Under no circumstances should the investigator contact Novartis or its agents, if any, monitoring the study to request approval of a protocol deviation, as no authorized deviations are permitted. If the investigator feels a protocol deviation would improve the conduct of the study this must be considered a protocol amendment, and unless such an amendment is agreed upon by Novartis and approved by the IRB/IEC/REB it cannot be implemented. All significant protocol deviations will be recorded and reported in the CSR.

### **12.1 Amendments to the protocol**

Any change or addition to the protocol can only be made in a written protocol amendment that must be approved by Novartis, Health Authorities where required, and the IRB/IEC/REB. Only amendments that are required for patient safety may be implemented prior to IRB/IEC/REB approval. Notwithstanding the need for approval of formal protocol amendments, the investigator is expected to take any immediate action required for the safety of any patient included in this study, even if this action represents a deviation from the protocol. In such cases, Novartis should be notified of this action and the IRB/IEC at the study site should be informed according to local regulations (e.g. UK requires the notification of urgent safety measures within 3 days) but not later than 10 working days.

## **14 Appendices**

### **14.1 Appendix 1 - Concomitant medications**

In general, the use of any concomitant medication deemed necessary for the care of the patient is permitted in this study, except as specifically prohibited below. Combination administration of study drugs could result in drug-drug interactions (DDI) that could potentially lead to reduced activity or enhanced toxicity of the concomitant medication and/or LEE011 and/or tamoxifen.

The following lists are not comprehensive and are only meant to be used as a guide. The lists are based on the Oncology Clinical Pharmacology guidance, Drug-Drug Interaction and Co-Medication Considerations (v07, release date: Jan 2018), which was compiled from the Indiana University School of Medicine's P450 Drug Interaction Table ([medicine.iupui.edu/clinpharm/ddis/main-table/](http://medicine.iupui.edu/clinpharm/ddis/main-table/)) and supplemented with the FDA Draft Guidance for Industry, Drug Interaction Studies – Study Design, Data Analysis, and Implications for Dosing and Labeling (February 2012) ([fda.gov/downloads/drugs/guidancecomplianceregulatoryinformation/guidances/ucm292362.pdf](http://fda.gov/downloads/drugs/guidancecomplianceregulatoryinformation/guidances/ucm292362.pdf)), and the University of Washington's Drug Interaction Database ([druginteractioninfo.org/](http://druginteractioninfo.org/)). For current lists of medications that may cause QT prolongation and/or torsades de pointes (TdP), refer to the CredibleMeds® website ([qtdrugs.org/](http://qtdrugs.org/)). Please contact the medical monitor with any questions.

**Table 14-1 List of prohibited medications during study drug treatment**

Category	Drug Name
Strong CYP3A4/5 inhibitors	Atazanavir/ritonavir, boceprevir, clarithromycin, cobicistat, conivaptan, danoprevir/ritonavir, darunavir/ritonavir, elvitegravir/ritonavir, grapefruit juice, idelalisib, indinavir, indinavir/ritonavir, itraconazole, ketoconazole, lopinavir/ritonavir, mibefradil, nefazodone, nelfinavir, ombitasvir/paritaprevir/dasabuvir/ritonavir (VIEKIRA PAK), posaconazole, ritonavir, saquinavir/ritonavir, telaprevir, telithromycin, tipranavir/ritonavir, troleandomycin, voriconazole
Strong CYP3A4/5 inducers	Apalutamide, avasimibe  , carbamazepine, enzalutamide, lumacaftor, mitotane, phenobarbital, phenytoin  , rifabutin, rifampin (rifampicin)  , St. John's wort (hypericum perforatum) 
Strong CYP2D6 inhibitors or inducers (for patients receiving tamoxifen)	Bupropion, dacomitinib, fluoxetine, paroxetine, quinidine
CYP3A4/5 substrates with NTI 	Alfentanil, astemizole, cisapride, cyclosporine, diergotamine, (dihydroergotamine), ergotamine, fentanyl, lomitapide  , lovastatin, nicardipine, nisoldipine, pimozide, quinidine, simvastatin, sirolimus, tacrolimus
Medications with a known risk for QT prolongation 	Amiodarone, anagrelide, arsenic trioxide, astemizole, azithromycin, bepridil, chloroquine, cocaine, chlorpromazine, cilostazol, ciprofloxacin, cisapride, citalopram, clarithromycin, disopyramide, dofetilide, domperidone, donepezil, dronedarone, droperidol, erythromycin, escitalopram, flecainide, fluconazole, gatifloxacin, grepafloxacin, halofantrine, haloperidol, ibutilide, levofloxacin, levomepromazine, levosulpiride, levomethadyl, mesoridazine, methadone, moxifloxacin, ondansetron, oxaliplatin, papaverine HCl (intra-coronary), pentamidine, pimozide, probucol, procainamide, propofol, quinidine, roxithromycin, sevoflurane, sotalol, sparfloxacin, sulpiride, sultopride, terlipressin, terodiline, terfenadine, thioridazine, vandetanib
CYP2C9 with NTI (for patients receiving tamoxifen)	Warfarin, coumarin anticoagulants
Herbal preparations/medications or dietary supplements	Herbal preparations/medications or dietary supplements known as strong inducers or inhibitors of CYP3A4/5 or those with a known risk of QT prolongation are prohibited throughout the study. These include, but are not limited to: St. John's wort, Kava, ephedra (ma huang), ginkgo biloba, dehydroepiandrosterone (DHEA), yohimbe, saw palmetto, black cohosh and ginseng. Patients should stop using these herbal medications or dietary supplements 7 days prior to first dose of study drug.
Other investigational and antineoplastic therapies	Other investigational therapies must not be used while the patient is on the study. Anticancer therapy (chemotherapy, hormonal therapy, including but not limited to all SERMS [including raloxifene], biologic or radiation therapy [except for palliative radiotherapy as outlined in the protocol], and surgery) other than the study treatments must not be given while the patient is on the study medication. If such agents are required, then the patient must discontinue study drug.

Category	Drug Name

 NTI = narrow therapeutic index drugs whose exposure-response indicates that increases in their exposure levels by the concomitant use of potent inhibitors may lead to serious safety concerns (e.g., Torsades de Pointes) or drugs which have <2-fold difference in the minimum toxic concentrations and minimum effective concentrations in the blood..
 
 Herbal product
 
 P-gp inducer
 
 The list provided is as of December 2019. Check https://www.crediblemeds.org/healthcare-providers/drug-list for the most updated list.
 
 Drug has warning for risk of hepatotoxicity. As far as possible, avoid co-administration of QT prolonging drugs or any other drugs with the potential to increase the risk of drug-related QT prolongation (e.g., via a potential DDI that increases the exposure of ribociclib or the exposure of the QT prolonging drug). A definitive list of drugs with a known risk, possible risk, or conditional risk of QT prolongation and/or Torsades de Pointes (TdP) is available online at qtdrugs.org.
 
Source: Novartis PK Sciences Memorandum: Drug-Drug Interactions (DDI) and Co-medication Considerations for Novartis Clinical Trials (January 2018), which is compiled from Indiana University "Clinically Relevant" Flockhart Table™, University of Washington Drug Interaction Database, and FDA Drug Development and Drug Interactions: Table of Substrates, Inhibitors and Inducers.
	

**Table 14-2 List of medications to be used with caution during study drug treatment**

Category	Drug Name
Moderate CYP3A4/5 inhibitors	Aprepitant, amprenavir, asafoetida resin (Ferula asafoetida), cimetidine, crizotinib, diltiazem, faldaprevir, imatinib, isavuconazole, netupitant, nilotinib, tofisopam, Schisandra sphenanthera (nan wu wei zi), verapamil
Moderate CYP3A4/5 inducers	Bosentan, dabrafenib, efavirenz, etravirine, genistein, lopinavir  , modafinil, nafcillin, telotristat
Sensitive CYP3A4/5 substrates 	Alpha-dihydroergocryptine, apixaban, aprepitant, atorvastatin, avanafil, bosutinib, brotizolam, budesonide, buspirone, cannabinoids  , cannabidiol  , cobimetinib, darifenacin, dasatinib, ebastine, eletriptan, eplerenone, everolimus, grazoprevir, ibrutnib, isavuconazole, ivabradine ivacaftor, lumefantrine, lurasidone, maraviroc, midazolam, perospirone, quetiapine, ridaforolimus, rivaroxaban, sildenafil, simeprevir, ticagrelor, tilidine, tolvaptan, triazolam, ulipristal, vardenafil, venetoclax, vicriviroc, voclosporin
BSEP inhibitors	Alectinib, atorvastatin, bromocriptine, candesartan, clobetasol, clofazimine, dabigatran, dipyridamole, glyburide, grazoprevir, ledipasvir, mifepristone, pioglitazone, reserpine, rifamycin, simeprevir, telmisartan, timcodar, troglitazone, velpatasvir
MATE1/2 substrates 	Acyclovir, cephalexin, cimetidine, fexofenadine, ganciclovir, glycopyrronium, metformin, pindolol, pliscainide, ranitidine, topotecan, varencicline
OCT1/2 substrates 	Amantadine, carboplatin, cisplatin, cephalexin, cephradine, ipratropium, lamivudine, linagliptin, metformin, oxyplatin, oxybutynin, phenformin, picoplatin, pilsicainide, pindolol, ranitidine, sorafenib, tropisetron, trospium, umecldinium, and zidovudine
BCRP substrates	Daunorubicin, dolutegravir, doxorubicin, hematoporphyrin, imatinib, methotrexate, mitoxantrone, pitavastatin, rosuvastatin, irinotecan, ethinyl estradiol, sulfasalazine, sofosbuvir, tenofovir, topotecan, venetoclax
Medications that carry a possible risk for QT prolongation 	Alfuzosin, apomorphine, aripiprazole, artemimol+piperazine, asenapine, atazanavir, atomoxetine, bedaquiline, bendamustine, bortezomib, bosutinib, buprenorphine, cabozantinib, capecitabine, ceritinib, clomipramine, crizotinib, clozapine, cyamemazine (cyamepromazine), dabrafenib, dasatinib, degarilix, delamanid, desipramine, dexmedetomidine, dolasetron, efavirenz, eliglustat, epirubicin, eribulin mesylate, ezogabine (retigabine), famotidine, felbamate, fingolimod, flupentixol, gemifloxacin, granisetron, hydrocodone-ER, iloperidone, imipramine (melipramine), isradipine, ketanserin, lapatinib, lenvatinib, leuprolide, loperamide, lithium, melperone, midostaurin, mifepristone, mirabegron, mirtazapine, moexipril/HCTZ, necitumumab, nilotinib, norfloxacin, nortriptyline, nusinersen, ofloxacin, olanzapine, osimertinib, oxytocin, paliperidone, palonosetron, panabinostat, pasireotide, pazopanib, perflutren lipid microspheres, perphenazine, pilsicainide, pimavanserin, pipamperone, promethazine, prothipendyl, quetiapine, ranolazine, rilpivirine, risperidone, romidepsin, sertindole, sorafenib, sunitinib, tamoxifen, telavancin, tetrabenazine, tipiracil/trifluridine, tizanidine, tolterodine, toremifene, trimipramine, tropisetron, vardenafil, vemurafenib, venlafaxine, vardenafil, ziprasidone
CYP2C19 or CYP2A6 substrates with NTI (for patients receiving letrozole)	S-mephenytoin
CYP2C9 or CYP2D6 with NTI (for patients receiving tamoxifen)	Phenytoin

Category	Drug Name

 Sensitive substrates include drugs whose plasma AUC values have been shown to increase 5-fold or higher when co-administered with a potent inhibitor.
 
 The list provided is as of January 2018. Check crediblemeds.org/healthcare-providers/drug-list for the most updated list.
 
 MATE1 and MATE2 share considerable substrate specificity.
 
 OCT1 and OCT2 share considerable substrate specificity.
 
 Lopinavir and atazanavir are prohibited when combined with ritonavir (see Table 14-1)
 
 Based on data that, exposure of cannabidiol (CBD), tetrahydrocannabinol (THC), 11-hydroxy THC, increased by ~2-3 folds when co-administered with ketoconazole (CYP3A4 inhibitor); Stott et al, Springerplus. 2013; 2: 236
 
Source: Novartis PK Sciences Memorandum: Drug-Drug Interactions (DDI) and Co-medication Considerations for Novartis Clinical Trials (January 2018), which is compiled from Indiana University "Clinically Relevant" Flockhart Table™, University of Washington Drug Interaction Database, and FDA Drug Development and Drug Interactions: Table of Substrates, Inhibitors and Inducers.
	

ENGLISH

During the past week:	Not at All	A Little	Quite a Bit	Very Much
17. Have you had diarrhea?	1	2	3	4
18. Were you tired?	1	2	3	4
19. Did pain interfere with your daily activities?	1	2	3	4
20. Have you had difficulty in concentrating on things, like reading a newspaper or watching television?	1	2	3	4
21. Did you feel tense?	1	2	3	4
22. Did you worry?	1	2	3	4
23. Did you feel irritable?	1	2	3	4
24. Did you feel depressed?	1	2	3	4
25. Have you had difficulty remembering things?	1	2	3	4
26. Has your physical condition or medical treatment interfered with your family life?	1	2	3	4
27. Has your physical condition or medical treatment interfered with your social activities?	1	2	3	4
28. Has your physical condition or medical treatment caused you financial difficulties?	1	2	3	4

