## **6.4 Concomitant medications**

### **6.4.1 Permitted concomitant therapy**

Medications required to treat AEs, manage cancer symptoms, concurrent diseases and supportive care agents, such as pain medications, anti-emetics and anti-diarrheals are allowed. Please consult the list of prohibited medications and the list of use with caution medications for further guidance.

The patient must be told to notify the investigational site about any new medications she takes after the start of the study treatment. All medications (other than study drugs) and significant non-drug therapies (including vitamins, herbal medicines, physical therapy and blood transfusions) administered within 30 days of study entry and during the study must be listed on the Concomitant medications/Significant non-drug therapies eCRF.

If patients take concomitant medications chronically, any change in dose or schedule of any concomitant medication throughout the study period should be clearly documented.

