#### **6.4.2 Concomitant therapy requiring caution**

Medications to be used with caution during combined LEE011/placebo, tamoxifen/NSAI, and goserelin treatment in this study are listed below (see [Table 14-2](#) in [Appendix 1](#), this list is not comprehensive and is only meant to be used as a guide. Please contact the medical monitor with any questions). These medications should be excluded if possible. If they must be given based on the investigator's judgment, then use with caution and consider a LEE011/placebo interruption if the concomitant medication is only needed for a short time:

- Moderate inhibitors or inducers of CYP3A4/5 (may increase or decrease LEE011 exposure, respectively)

- Sensitive substrates of CYP3A4/5 that do not have narrow therapeutic index (LEE011 may increase exposure to these medications)
- Inhibitors of BSEP (based on *in vitro* data co-administration with LEE011 may lead to intrahepatic cholestasis)
- Medications that carry a possible risk for QT prolongation (may precipitate QT prolongation and TdP)
- Sensitive substrates of the renal transporters, MATE1/2 substrates and OCT1/2 substrates (LEE011 has the potential to increase exposure to substrates of these transporters, although no animal or clinical data are available to support these statements)
- Sensitive substrates of BCRP (LEE011 has the potential to increase exposure to substrates of these transporters, although no animal or clinical data are available to support these statements)
- Substrates metabolized predominantly by CYP2C9 or CYP2D6 with a narrow therapeutic index (that could be affected by tamoxifen)
- Substrates metabolized predominantly by CYP2C19 or CYP2A6 with a narrow therapeutic index (that could be affected by letrozole)

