#### 6.4.3 Prohibited concomitant therapy

The following medications are prohibited during combined LEE011/placebo, tamoxifen/NSAI, and goserelin treatment in this study (Table 14-1 in Appendix 1, this list is not comprehensive and is only meant to be used as a guide. Please contact the medical monitor with any questions):

- Strong inhibitors or inducers of CYP3A4/5 (may significantly increase or decrease LEE011 exposure, respectively)
- Substrates of CYP3A4/5 with a narrow therapeutic index (LEE011 may increase exposure to these medications resulting in toxicity to these medications)
- Medications with a known risk for QT prolongation and/or TdP (may precipitate QT prolongation and TdP in combination with LEE011)
- Additionally, for patients receiving tamoxifen: strong inhibitors or inducers of CYP2D6 (that could affect tamoxifen exposure)
- Warfarin and coumarin derivatives (for patients receiving tamoxifen)
- Other investigational and antineoplastic therapies
- Herbal preparations/medications and dietary supplements that are strong inhibitors or inducers of CYP3A4/5 or those with a known risk of QT prolongation. These include but are not limited to: St. John's wort, Kava, ephedra (ma huang), ginkgo biloba, dehydroepiandrosterone (DHEA), yohimbe, saw palmetto, black cohosh and ginseng. Patients should stop using these preparations/ medications at least 7 days prior to first dose of study treatment.

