#### **7.1.5.1 Discontinuation of study treatment**

Patients **may** voluntarily discontinue from the study treatment for any reason at any time.

If a patient decides to discontinue from the study treatment, the investigator must make reasonable effort (e.g. telephone, e-mail, letter) to determine the primary reason for this decision and record this information in the patient's chart and on the appropriate CRF pages. They may be considered withdrawn if they state an intention to withdraw, fail to return for visits, or become lost to follow-up for any other reason.

The investigator should discontinue study treatment for a given patient if, he/she believes that continuation would be detrimental to the patient's well-being.

Patients may be withdrawn from the study treatment if any of the following occur:

- Adverse Event (including, but not limited to  $QTcF \geq 501$  msec, confirmed at repeated ECG measurements and recurrent after dose adjustment was performed; documented episode of ventricular tachycardia, or ventricular fibrillation)
- Lost to follow-up
- Physician decision
- Progressive Disease

- Protocol deviation
- Study terminated by sponsor
- Technical problems

Patients must be withdrawn from the study treatment if any of the following occur:

- Pregnancy
- Death
- Subject/Guardian decision

In addition to the general withdrawal criteria, the following study specific criteria will also require study treatment discontinuation:

- Adjustments to study treatment that result in discontinuation. Please refer to [Section 6.3](#).
- Use of prohibited medication. Please refer to [Section 6.4.3](#).

Patients who discontinue study treatment should NOT be considered withdrawn from the study. They should return for the assessments indicated in [Section 7.1](#). If they fail to return for these assessments for unknown reasons, reasonable effort (e.g. telephone, email, letter) should be made to contact them as specified in [Section 7.1.5](#).

Patients who discontinue study treatment should undergo an End of Treatment (EOT) visit followed by a 30 day safety follow-up.

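### Phenytoin is prohibited for every patient in Table 14-1, yet it is the only drug in Table 14-2's use-with-caution row for patients on tamoxifen

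*Protocol*

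**What the plan says.** Appendix 1 of the protocol has two drug lists. In Table 14-1 (prohibited), the strong CYP3A4/5 inducer row includes "carbamazepine, enzalutamide, lumacaftor, mitotane, phenobarbital, phenytoin". Section 6.4.3 states the same ban by class: "Strong inhibitors or inducers of CYP3A4/5 (may significantly increase or decrease LEE011 exposure, respectively".

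Table 14-2 (use with caution) has a row headed "CYP2C9 or CYP2D6 with NTI (for patients receiving tamoxifen". Phenytoin is the only drug in it. Section 6.4.2 asks sites to avoid drugs on this list where they can. If the investigator judges one necessary, the instruction is "then use with caution and consider a LEE011/placebo interruption if the concomitant medication is only needed for a short time".

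Section 6.4.1 points sites to both lists: "Please consult the list of prohibited medications and the list of use with caution medications for further guidance". Section 7.1.5.1 introduces a set of mandatory stopping reasons with "the following study specific criteria will also require study treatment discontinuation", and use of a prohibited medication is one of them.

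**The concern.** The same drug carries two incompatible instructions in current protocol text. A site with a tamoxifen patient who needs an anticonvulsant could look up the tamoxifen rows, find phenytoin under caution, and start it. By Table 14-1 and Section 7.1.5.1 that patient must then come off study treatment, because her site followed a table in the protocol.

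The tamoxifen rows also invite that reading. Among narrow-index CYP2C9 substrates, Table 14-1 prohibits warfarin and coumarins for tamoxifen patients, while Table 14-2 puts phenytoin under caution. Seen side by side, phenytoin looks like the one that was deliberately allowed.

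The row also points to the patients in whom a strong inducer could act on two study drugs, LEE011 and tamoxifen.

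**Working it through.** The plan states no figure on this point, so the check sets the relevant text side by side and then bounds the number of patients concerned.

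**1. Whom the prohibition covers.** In Table 14-1, the strong CYP2D6 row and the CYP2C9 narrow-index row are expressly limited to patients receiving tamoxifen. The strong CYP3A4/5 inducer row has no such limit, and neither does the matching bullet in Section 6.4.3. Exclusion criterion 13 in Section 5.3 bars the class at entry unless it can be stopped 7 days before treatment. The ban therefore covers every patient, including those on tamoxifen.

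**2. The two instructions for a tamoxifen patient.**

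| | Table 14-1 with Sections 6.4.3 and 7.1.5.1 | Table 14-2 with Section 6.4.2 |
|---|---|---|
| Reason listed | Strong CYP3A4/5 inducer | Narrow-index CYP2C9/CYP2D6 substrate |
| Patients | All | Those on tamoxifen |
| May it be given? | No | Yes, if the investigator judges it necessary |
| If given | Study treatment must stop | Caution; consider interrupting LEE011/placebo for short use |

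**3. Which entry governs.** The introduction to Appendix 1 permits necessary co-medication "except as specifically prohibited below". A drug prohibited by name falls under that exception. Section 2.4 of the primary-analysis SAP points the same way: it takes prohibited substances from Table 14-1 and records their use as protocol deviations. The prohibition governs, so the Table 14-2 entry is the one to correct.

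**4. Whether the protocol resolves it.** Footnote 5 of Table 14-2 deals with one overlap between the tables: "Lopinavir and atazanavir are prohibited when combined with ritonavir", with a pointer to Table 14-1. Phenytoin has no note. Quinidine also acts by several mechanisms, but its three listings are all in Table 14-1, so it is prohibited each time. No sentence says which table takes precedence.

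**5. How many patients.** The Amendment 7 summary gives 114 patients on treatment: 79 in the ribociclib arm and 35 in the placebo arm, of whom 8 had crossed over. Section 6.1 requires crossover patients to be on an NSAI.

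- Placebo-arm patients who could still be on tamoxifen: 35 − 8 = 27
- Upper bound on tamoxifen: 79 + 27 = 106
- Of these, in the ribociclib arm: at most 79

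These are ceilings, because they treat every patient who did not cross over as being on tamoxifen.

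**6. Evidence on exposure.** Section 1.2.1.5 reports that rifampicin, a strong CYP3A4 inducer, cut LEE011 AUC by 89%. Section 1.6.1 reports lower concentrations of tamoxifen and its metabolites with strong CYP3A4/5 inducers. Both are class evidence. The documents give no exposure data for phenytoin itself.

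**The case against.** The best case on the other side is that this is an editorial cross-listing which a careful reader resolves without help.

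- **The tables sort by mechanism.** Phenytoin is both an inducer and a narrow-index substrate, so it can properly appear under both. Table 14-2 also lists anticancer drugs such as cisplatin, doxorubicin and capecitabine, although Table 14-1 bans other anticancer therapy as a class. A Table 14-2 entry is thus an interaction flag, not permission. This stands in part, and it favours a general precedence line. But phenytoin is banned by name, and it is all that its caution row contains.
- **The lists are described as incomplete guides, with a medical monitor for questions.** That helps with drugs missing from the lists. It does not tell a site that a listed drug has a contrary listing elsewhere.
- **Footnote 5 is not an exact precedent.** It covers drugs whose status changes when combined with ritonavir, not drugs banned outright. This is correct. The footnote shows only that the authors saw a need to reconcile the tables.
- **The SAP support is dated.** Section 2.4 belongs to the primary-analysis SAP, written against Amendment 4. The final SAP, written against Amendment 7, has no such section. This stands. The conclusion on precedence rests on the protocol; the SAP only agrees with it.
- **The exposure argument is weaker than it looks.** Section 1.3 says the tamoxifen label requires no dose adjustment with strong CYP3A4 inducers. Up to 27 of the 106 patients are in the placebo arm and take no LEE011. Both points stand and narrow the exposure risk mainly to LEE011 in the ribociclib arm.

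**Conclusion.** The concern holds. The current protocol prohibits phenytoin for all patients in one table and allows it with caution for tamoxifen patients in another, with nothing to reconcile the two. This is an internal inconsistency in an operational safety table. It does not touch alpha, power, the endpoints or any formal analysis: PFS and OS had both been met, and Section 10.7.2 makes later analyses descriptive.

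The practical size is small. It rests on the Amendment 7 treatment counts and on the assumption that the stricter listing is the intended one, which the rest of the protocol supports. The actual tamoxifen split is unknown, as is whether any patient received phenytoin, so the realised effect may be nil. For a patient it did reach, the result could be reduced LEE011 exposure or an avoidable loss of study treatment.

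**What to change.** Delete phenytoin from Table 14-2, which removes the row. Alternatively, keep the row and add a footnote that phenytoin is prohibited under Table 14-1. A useful extra is one sentence in Appendix 1 saying that the prohibitions in Table 14-1 and Section 6.4.3 override any listing in Table 14-2. That would also settle the anticancer-drug overlap.

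The cost is one entry or one footnote in a table that the amendment log shows was already revised in Amendments 1, 2, 5 and 7. Data collection and analysis do not change.
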